#### **Pharmacogenomics, and Other Biomarker Analyses**

Not applicable.

#### **Safety Analyses**

All safety analyses will be performed on the SAF and will be presented by the study treatment. Safety data will be summarized descriptively. Data describing quantitative measures will be summarized as mean, SD, median and range (minimum and maximum). Qualitative variables will be presented as counts and percentages.

All safety data will also be displayed in listings.

#### **Other Analyses**

Not applicable.

## 1. LIST OF ABBREVIATIONS

**Table 1: List of Abbreviations**

Abbreviation	Term
AE	Adverse Event
AIC	Akaike Information Criteria
ANOVA	Analysis of Variance
AUC	Area Under the Plasma Concentration-time Curve
AR	Auto Regressive
BLQ	Below the Limit Quantification
BMI	Body Mass Index
CI	Confidence Interval
CV	Coefficient Variation
COPD	Chronic Obstructive Pulmonary Disease
CRF	Case Report Form
CS	Compound Symmetry
CSR	Clinical Statistical Report
CTCAE	Common Terminology Criteria for Adverse Events
ECG	Electrocardiogram
EDC	Electronic Data Collection
eCRF	Electronic Case Report Form
EDTA	Ethylenediaminetetraacetic Acid
FAS	Full Analysis Set
GCP	Good Clinical Practices
GFR	Glomerular filtration rate
IVRS	Interactive Voice Response System
IWRS	Interactive Web Response System
IRB	Institutional Review Board
J2R	Jump to Reference
LLOQ	Lower Limit of Quantitative
MMRM	Mixed-effect Model Repeated Measure
MedDRA	Medical Dictionary for Regulatory Activities Terminology
PD	Pharmacodynamics
%CV	Coefficient of Variation

PK	Pharmacokinetics
PKAS	Pharmacokinetics Analysis Set
PP	Per-Protocol Population
PT	Preferred Term
QCD	Quantitative Clinical Development
QD	Once Daily
SD	Standard Deviation
SAE	Serious Adverse Event
SAF	Safety Analysis Set
SAP	Statistical Analysis Plan
SOC	System Organ Class
TEAE	Treatment Emergent Adverse Event
TOEP	Toeplitz
VC	Variance Components

## 2. INTRODUCTION

The purpose of this statistical analysis plan (SAP) is to provide details of the planned statistical methodology for the analysis of the study data. The SAP also outlines the statistical programming specifications for the tables, listings and figures.

This SAP describes the study endpoints, derived variables, anticipated data transformations and manipulations, and other details of the analyses not provided in the study protocol. This SAP therefore outlines in detail all other aspects pertaining to the planned analyses and presentations for this study.

The following documents were reviewed in preparation of this SAP:

Protocol Revision Chronology:		
Protocol 1.0	11-Oct-2016	Original
Protocol 2.0	05-Jan-2017	Amendment 1
Protocol 3.0	11-Apr-2017	Amendment 2

This SAP was developed in accordance with ICH E9 guideline. All decisions regarding final analysis, as defined in this SAP document, will be made prior to Database Lock (unblinding) of the study data. Further information can be found in the protocol.

### **3. STUDY OBJECTIVES AND ENDPOINTS**

#### **3.1. Study Objectives**

##### **3.1.1. Primary Objective**

The primary objectives are:

- To assess the relative bioavailability of GSP304 (tiotropium bromide) Inhalation Solution at dose levels of [REDACTED] compared with Spiriva® Respimat® inhalation spray (5 µg QD) in subjects with COPD.
- To characterize the dose response of GPS304 at dose levels of [REDACTED] with respective PD.

##### **3.1.2. Secondary Objective**

The secondary objective is to assess the safety and tolerability of GSP304 at dose levels of [REDACTED]

#### **3.2. Study Endpoints**

##### **3.2.1. Primary Endpoints**

The primary endpoints are:

- The PK endpoints for tiotropium in plasma to assess the relative bioavailability are:
  - Peak concentrations during the dosing interval at steady-state ( $C_{maxSS}$ )
  - Area under the plasma concentration-time curve over the dosing interval at steady state ( $AUC_{0-\tau_{ass}}$ )
- Change from baseline (Day 1) at Day 21 (Week 3) in trough FEV1 response at approximately 24 hours after the last dose (average of 23 hours 15 minutes and 23 hours 45 minutes post-dose measurements), in comparison with GSP304 placebo

##### **3.2.2. Secondary Endpoints**

The secondary endpoints are:

- Amount ( $A_{etau}$ ) and fraction of dose of tiotropium ( $F_e$ ) excreted in urine over the dosing interval on Day 1 and Day 21
- Peak concentrations during the dosing interval ( $C_{max}$ ) on Day 1
- Area under the plasma concentration-time curve over the dosing interval ( $AUC_{0-\tau}$ ) on Day 1

- Time of peak drug concentration over the dosing interval ( $t_{max}$ ) on Day 1 and Day 21
- Average concentration during a dosing interval at steady state ( $C_{avSS}$ ) on Day 21
- Accumulation ratio ( $R_{ac}$ )
- Change from baseline in peak  $FEV_1$  within 12 hours post-dose on Day 1 and Day 21
- Change from baseline (Day 1) at Day 21 (Week 3) in trough  $FEV_1$  response at approximately 24 hours after the last dose (average of 23 hours 15 minutes and 23 hours 45 minutes post-dose measurements), in comparison with GSP304 placebo
- Change from baseline in time-normalized area under the curve for  $FEV_1$  measured over 12 hours on Day 1 and Day 21
- Time to onset of response, defined as at least 12% and 200 mL increase in  $FEV_1$  within 12 hours of dosing on Day 1
- Time to achieving steady state as measured by  $FEV_1$  trough assessments
- Time to achieving steady state as measured by FVC trough assessments

### **3.2.3. Safety Endpoints**

The safety endpoints are:

- Vital signs, laboratory parameters, 12-lead ECG
- Incidence of all AEs

## 4. STUDY DESIGN

### 4.1. Summary of Study Design

This is a phase 2, randomized, parallel group, active-and placebo-controlled, 5-arm study to compare the PK profile of 3 blinded doses of GSP304 with open label Spiriva® Respimat®. The study will also evaluate the dose response PD profile of 3 blinded doses of GSP304 compared with blinded GSP304 placebo, using spirometry in subjects with mild to moderate COPD.

The study will consist of a screening period of up to 2 weeks, followed by a 2-week run-in period, a 3-week treatment period, and a 2-week post treatment follow-up period. The total duration of study participation will be approximately 9 weeks.

A total of 155 male and female subjects will be randomized in a 1:1:1:1:1 ratio to 1 of 5 treatment arms. A subject will receive 1 of the 3 double-blind doses of GSP304, or double-blind GSP304 placebo, or open-label Spiriva® Respimat®.

### 4.2. Definition of Study Drugs

Table 2 and Table 3 provide a description of the double-blind GSP304, double-blind GSP304 placebo, and the open label Spiriva® Respimat® comparator to be used in the study.

**Table 2: GSP304**

Product name:	GSP304	GSP304	GSP304
Dosage Form:	Inhalation solution	Inhalation solution	Inhalation solution
Unit Dose	■■■	■■■	■■■
Route of Administration	Oral inhalation	Oral inhalation	Oral inhalation
Method of Administration	Nebulization	Nebulization	Nebulization
Physical Description	A clear solution in a semitransparent, soft plastic ampule	A clear solution in a semitransparent, soft plastic ampule	A clear solution in a semitransparent, soft plastic ampule

**Table 3: Other Study Drugs**

	Comparator Product	GSP304 Placebo
Product Name	Spiriva® Respimat®	Matching placebo for GSP304
Dosage Form	Inhalation spray for oral inhalation	Inhalation solution
Unit Dose	2.5 µg	0 µg
Route of Administration	Oral inhalation	Oral inhalation
Method of Administration	Metered spray for inhalation	Nebulization
Physical Description	A clear solution in a green/grey plastic Respimat® inhaler	A clear solution in a semi-transparent, soft plastic ampule
Manufacturer	Boehringer Ingelheim Pharma GmbH & Co	Glenmark or designee

### **4.3. Sample Size Considerations**

#### **4.3.1. Sample Size Justifications**

A sample size of 28 subjects per treatment arm will have 90% power to detect a difference in mean change from baseline in trough FEV1 of 150 mL between GSP304 and GSP304 placebo assuming a 2-sided alpha of 5% and a standard deviation (SD) of 170 mL. These assumptions are based on available literature from similar studies conducted for Spiriva® Respimat® (Caillaud et al., 2007). Given the overall 1:1:1:1:1 study treatment allocation ratio, 140 subjects are required for the analysis of the primary endpoint. Assuming a dropout rate of 10%, a total of 155 subjects (31 subjects per treatment arm) will be randomized.

This sample size is also considered to be sufficient for the relative bioavailability endpoint.

#### **4.3.2. Sample Size Re-estimation**

No sample size re-estimation is planned for this study.

### **4.4. Randomization**

Randomization and investigational product (IP) assignment will occur in the morning of Day 1 after all screening procedures have been performed, run-in has been completed and eligibility of the subject for the study confirmed. Randomization numbers will be issued centrally using interactive voice response system (IVRS)/interactive web response system (IWRS). Randomized

subjects who terminate their study participation for any reason, regardless of whether study drug has been taken or not, will retain their randomization number.

Subjects will be assigned in the ratio of 1:1:1:1:1 to receive treatments with either of double-blind GSP304 at 1 of 3 dose levels, open-label Spiriva® Respimat®, or double-blind GSP304 placebo based on a computer-generated randomization scheme that will be reviewed and approved by a statistician. The randomization scheme will be stored within the IVRS/IWRS database until unblinding of this study is requested. The randomization scheme and identification for each subject will be included in the final clinical study report for this study.

#### **4.5. Clinical Assessments**

The following clinical assessments will be performed during the study.

1. Vital signs: vital signs will be taken at screening (Day -28 to -15), Day -1, Day 1 (1 hour pre-dose and 1 hour post-dose), Day 2, Day 7, Day 14 (1 hour pre-dose and 1 hour post-dose), Day 20, Day 21 (post-dose), Day 22 (ie 24 hours after Day 21 dose), and Day 35 ( $\pm 2$ ; ie 2 weeks follow-up after last dose date).
2. Physical Examination: physical examination will be performed at screening (Day -28 to Day -15 (comprehensive physical examination)), Day -1 (ie, 24 hours before Day 1 dose), Day 7 (pre-dose), Day 14 (pre-dose), and Day 20 (pre-dose).
3. 12 Lead Electrocardiogram (ECG): 12 lead ECG will be performed at screening (Day -28 to Day -15), Day 1 (pre-dose) and Day 21 (pre-dose).
4. Laboratory Tests: hematology, biochemistry, and urine analysis tests will be performed at screening (Day -28 to Day -15), Day 7 (pre-dose), Day 14 (pre-dose), Day 21 (pre-dose), and Day 35 ( $\pm 2$ ; ie 2 weeks follow-up after last dose date). Urine analysis for drugs of abuse and cotinine and blood alcohol tests will be performed on screening (Day -28 to Day -15), Day -1, and Day 20 (pre-dose). Serum pregnancy testing will be performed in all female subjects on screening (Day -28 to Day -15), and urine pregnancy testing will be performed in female subjects on Day -1 and Day 35 ( $\pm 2$ ).
5. Other safety assessments consisting of monitoring and recording all Adverse Events, serious adverse events (SAEs) and Concomitant Medications will be collected throughout the study.
6. Pharmacodynamics: The spirometry test will be performed at screening (Day -28 to Day -15), Day 1 (pre-dose -45 mins and -15 mins), Day 7 (pre-dose -45 mins and -15 mins), Day 14 (pre-dose -45 mins and -15 mins), Day 21 (pre-dose -45 mins and -15 mins), and Day 22 (ie 24 hours after Day 21 dose). Pre-dose FEV1 and FVC will be assessed at -45 minutes and -15 minutes prior to dosing on Day 1, Day 7, Day 14, and Day 21. Trough FEV1 will be assessed on Day 22 (ie 24 hours after Day 21 dose). On Day 1 and Day 21,

FEV1 will be recorded, at the following time points after the morning dose: immediately post-dose at 5 minutes ( $\pm 3$  minutes), 15 minutes ( $\pm 2$  minutes), 30 minutes ( $\pm 5$  minutes), 60 minutes, 90 minutes, and 2 hours (120 minutes); and post-dose at 4, 6, 8, 10, 12, 23 hours 15 minutes and 23 hours 45 minutes post-dose. All post-dose timings are relative to the end of dosing (ie, end of nebulization of GSP304/GSP304 placebo or after the second actuation of Spiriva® Respimat®). The window for 1-hour spirometry and thereafter is  $\pm 5$  minutes.

7. Pharmacokinetic Plasma and Urine Concentrations: Blood samples (approximately 6 mL) will be collected in dipotassium ethylenediaminetetraacetic acid (EDTA) coated vacutainers on Day 1 and Day 21 according to the below schedule: Pre-dose (0 hour), and 2, 4, 6, 10, 15, 30, 45, 60, 75, and 90 minutes post-dose, as well as 2, 4, 6, 8, 12, 16, 20 and 24 hours post-dose. All post-dose timings are relative to the end of dosing (ie, end of nebulization of GSP304/GSP304 placebo or after the second actuation of Spiriva® Respimat®). The pre-dose sample on Day 1 should be collected within 30 minutes prior to dosing while on Days 7, 14, and 21 the pre-dose sample should be collected within 10 minutes prior to the morning dose.

On Day 1 and Day 21, samples will be collected within the following collection windows:

- For the 2 minute sample, within a window of  $\pm 30$  seconds
- For the 4, 6, 10, 15, and 30 minute samples, within a window of  $\pm 1$  minute
- For the 45, 60, 75, 90 minute, and 2.0 hour samples, within a window of  $\pm 2$  minutes
- For the 4, 6, 8, 12, 16, 20 and 24 hour samples, within a window of  $\pm 5$  minutes.

In addition, urine will be collected into pre-weighed containers at pre-dose (within 1 hour prior to dosing), and at the following intervals post-dose from 0-6, 6-12, and 12-24 hours on Day 1 and Day 21.

Collection times and the accurate volume of urine will be noted. In each urine container, approximately 5 mL of 1M citric acid must be added prior to start of collection. Plasma and urine concentrations of tiotropium will be quantified by a validated liquid chromatography-mass spectrometry method.

Plasma: Plasma PK parameters will be determined from plasma concentrations using non-compartmental methods for each subject. Actual collection times will be used for the analyses.

Urine: Amount and fraction of dose of tiotropium excreted in urine during the collected time interval in individual subjects will be estimated. Nominal collection times and urine volumes will be used for the estimation.

## **5. PLANNED ANALYSES**

### **5.1. Interim Analyses**

No interim analyses are planned for this study.

### **5.2. Final Analyses**

All planned analyses will be carried out once the clinical database lock (DBL) has taken place. Once this has been achieved, unblinding will occur and the analyses will be performed.

## **6. GENERAL CONSIDERATIONS FOR DATA ANALYSES AND HANDLING**

### **6.1. General Summary Table and Individual Subject Data Listing Consideration**

In general, listings will be sorted and presented by treatment and subject number. Subject number when broken down consists of the site number and 4 digits sequential number. Study visits will be labeled as Screening, Baseline (Day 1), Day 2, Day 7, Day 14, Day 20 and Day 21 as well as End of Study (Follow Up) and Unscheduled. When required, the time of the scheduled assessment will be included.

The following treatment levels will be used for all tables, figures, and listings in the order below. Spiriva R will be used for Spiriva® Respimat® in tables, figures and listings for simplicity.

GSP304 [REDACTED]
GSP304 [REDACTED]
GSP304 [REDACTED]
GSP304 Total (AE/SAE-related tables)
GSP304 Placebo
Spiriva R 5 µg

### **6.2. General Post Text Summary Table and Individual Subject Data Listing Format Considerations**

Tables, figures and listings are numbered following the ICH structure. Table headers, variables names and footnotes will be modified as needed following data analyses. Additional tables, figures and listings will be generated, as needed, following the data analysis (post-hoc).

### **6.3. Data Management**

Data from the study will be managed by the Sponsor's Clinical Research Operations group or designee. The Investigator will allow representatives of the Sponsor, regulatory agencies, and their designees to inspect all study documents (including, but not limited to, consent forms, IP accountability forms, IRB/IEC approvals) and pertinent hospital or clinic records for confirmation of data throughout and after completion of the study. Monitoring visits will be

conducted as needed during the course of the study. A complete review of source documentation of key efficacy and safety data will be conducted at each monitoring visit for verification that all information recorded in the CRF/eCRF accurately reflects the data recorded in the subject's source documents.

All data verification, using hospital or clinic records, will be performed respecting subject confidentiality and will be carried out in accordance with SOPs.

All subject data generated during the study will be recorded and transcribed into a database. The final authorization of the CRF/eCRF data is the Investigator Signature Form. This form must be approved by the Principal Investigator to signify that he/she has reviewed the CRF/eCRF, including all laboratory and safety assessments, and that all of the data therein is complete and accurate.

The data will be reviewed to ensure that the forms were completed properly.

Datasets will be prepared using headings from Clinical Data Interchange Consortium (CDISC) Study Data Tabulation Model (SDTM) implementation for human clinical trials and ADaM (Analysis Dataset Model).

All tables, figures and listings will be produced using SAS® statistical software Version 9.3 or a later version, unless otherwise noted in a secure and validated environment. Each output will be provided in PDF format, with all tables and listings also being produced in RTF format.

All analyses will be performed using SAS® Version 9.3 in a secure and validated environment. All tables, figures and data listings to be included in the report will be independently checked for consistency, integrity and in accordance with standard PAREXEL procedures.

#### **6.4. Data Presentation Conventions**

Continuous data will be summarized in terms of the mean, SD, median, minimum, maximum, and number of observations, unless otherwise stated. Continuous data that are expected to be skewed will be presented in terms of the maximum, upper quartile, median, lower quartile, minimum, and number of observations. The minimum and maximum will be reported to the same number of decimal places as the raw data recorded in the database. The mean, median, lower quartile and upper quartile will be reported to one more decimal place than the raw data recorded in the database. The SD will be reported to two more decimal places than the raw data recorded in the database. In general, the maximum number of decimal places reported shall be four for any summary statistic.

Categorical data will be summarized in terms of the number of subjects providing data at the relevant time point (n), frequency counts, and percentages. Any planned collapsing of categories will be detailed in the corresponding sections of this SAP and within the data displays.

Percentages will be presented to one decimal place. Percentages will not be presented for zero counts.

Percentages will be calculated using n as the denominator.

Changes from baseline in categorical data will be summarized using shift tables where appropriate.

P-values greater than or equal to 0.001, in general, will be presented to three decimal places. P-values less than 0.001 will be presented as “<0.001” and p-values greater than 0.999 will be presented as “>0.999”.

Confidence intervals will be presented to one more decimal place than the raw data.

A table, figure, listing is to be generated for any required item where no data is available or reported, with either a table or listing stating “No Data Available” or “No Data Reported”, or print a one line message indicating there was no report data available: “NO DATA AVAILABLE FOR THIS REPORT”.

## **6.5. Analysis Sets**

### **6.5.1. Full Analysis Set (FAS)**

This will include all subjects who are randomized, have received at least 1 dose of study medication and have at least 1 post-baseline PD assessment. This analysis set will be the primary analysis set for the PD endpoints.

### **6.5.2. Safety Set (SAF)**

This will include all subjects who are randomized and received at least 1 dose of study medication. All safety endpoints will use the SAF.

### **6.5.3. Per-Protocol Set (PP)**

This will include all subjects who are randomized, received at least 1 dose of study medication, completed the study and do not have exclusionary major protocol deviations. Major and exclusionary protocol deviations will be defined in section 7.3 and by clinical review prior to unblinding.

#### **6.5.4. Pharmacokinetic Set (PKAS)**

This will include all subjects who are randomized, received at least 1 dose of study treatment and have at least 1 quantifiable PK sample and do not have exclusionary major protocol deviations. The PKAS will be used to analyze the PK endpoints unless otherwise specified in this SAP. Major and exclusionary protocol deviations will be defined in section 7.3 and by clinical review prior to unblinding.

Subjects or data may be excluded from the PKAS at the discretion of the PK Scientist upon consultation with the sponsor. Any data excluded will be discussed in the CSR. Any excluded subject will have his or her concentration and PK parameter data (if available) listed only. Subjects who receive placebo will not be part of the PKAS. The PKAS will be used for all tables and graphical summaries of the PK data

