#### Considerations in the handling of BLQ data for the generation of plasma PK Parameters and for plotting of individual plasma PK concentration data

BLQ values will be imputed in the PK concentration dataset used for the derivation of PK parameters. The following rules will be applied:

- BLQs at the beginning of a subject profile (ie before the first incidence of a measurable concentration on the first day of dosing) will be assigned to zero;
- BLQs at the end of a subject profile (ie after the last incidence of a measurable concentration on last day of dosing) will be set to missing;
- Single or consecutive BLQs which fall between measurable concentrations will be set to missing.
- Quantifiable concentrations falling between two BLQ values might be set to missing if considered anomalous by the PK Scientist after consultation with the sponsor.

For linear plots, zero concentration value(s) will be included in the plot while missing values will be ignored. For log-linear plots, zero concentration value(s) will be assigned a  $\frac{1}{2}$  LLOQ value with the exception of the pre-dose sample collected on Day 1 while missing concentrations at the end of the profile will be ignored.

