- $A_{\tau_{avSS}}$  is the cumulative amount excreted over the dosing interval and will be calculated as the sum of the products of concentration and urine volume over the appropriate collection intervals. For the calculation of urine PK parameters the protocol time intervals should be used. If a subject urinates into the toilet or a urine sample is lost any other way, or if no urine volume has been recorded for a sampling interval, the cumulative amount excreted starting with this interval cannot be calculated. If, however, a subject is unable to urinate, no amount excreted has been lost and the cumulative amount can continue to be calculated past that collection interval. For the affected time interval, the partial amount will be zero;
- $Fe\%$  is the fraction of unchanged drug in urine expressed as a percentage and will be calculated as  $Fe\% = (A_{\tau_{avSS}} / Dose) * 100$ .

If  $t_{last}$  (last time point with measurable concentration) is before 24 hour post-dose in more than

50% of treated subjects s at any particular dose of GSP 304 or Spiriva® Respimat®, AUClast (area under the plasma concentration time curve from time zero to last time point with measurable concentration) may be estimated and compared between different doses of GSP 304 and Spiriva® Respimat® by ANOVA.

Any inconsistency between plasma and urine PK would be will be further investigated and might be flagged and/or excluded from the analysis at the discretion of the PK Scientist after consultation with the sponsor.

An exploratory PK/ glomerular filtration rate (GFR) analysis of GSP304 in urine and plasma may be performed if deemed appropriate following review of the summary PK and GFR data. The decision to perform this analysis will be made by the Sponsor upon review of the tables, figures and listings produced at the end of the study. If the decision is made not to proceed with the PK/ GFR analysis, this section of the SAP will not be applicable and the outputs described herein will not be presented.

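### Discretionary exclusions from the primary PK analysis have no objective criterion, and no analysis shows their effect on the bioavailability ratios

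*SAP*

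**What the plan says.** Section 8.4 makes the ratios of CmaxSS and AUC0-tauSS, each GSP304 dose against Spiriva Respimat, the primary PK result. They come from an ANOVA on ln-transformed values and carry 90% confidence intervals. Section 8.3 plans no formal test.

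Four places allow discretionary exclusion:

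- Section 6.5.4: "Subjects or data may be excluded from the PKAS at the discretion of the PK Scientist upon consultation with the sponsor".
- Section 6.7.6.1, on values below quantification: "Quantifiable concentrations falling between two BLQ values might be set to missing if considered anomalous by the PK Scientist", again after consulting the sponsor.
- Section 6.7.6.2, on incomplete profiles: inclusion depends on whether CmaxSS or AUC0-tauSS can be reliably calculated, and is settled case by case by the PK Scientist with the sponsor.
- Section 6.7.6.2, on disagreement between plasma and urine results: after further investigation these "might be flagged and/or excluded from the analysis at the discretion of the PK Scientist after consultation with the sponsor".

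On timing, section 6.5.4 says of deviation-based exclusions: "Major and exclusionary protocol deviations will be defined in section 7.3 and by clinical review prior to unblinding". The general statement is in section 2: "All decisions regarding final analysis, as defined in this SAP document, will be made prior to Database Lock (unblinding) of the study data".

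On reporting, section 6.5.4 says "Any data excluded will be discussed in the CSR", then "Any excluded subject will have his or her concentration and PK parameter data (if available) listed only", and finally "The PKAS will be used for all tables and graphical summaries of the PK data". Listing 16.2.6.2.4 shows each excluded parameter with its value and a reason.

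**The concern.** An exclusion rule is harmless when it rests on something unrelated to the result, such as a failed nebulization or a mislabelled tube. The sentence in section 6.5.4 does not ask for that. The rules in section 6.7.6 can be applied only by someone looking at the concentrations or the parameters derived from them. An unusually high or low profile is the most likely to be called anomalous or inconsistent, and it is also the one with most influence on a geometric mean. Removing such profiles unevenly between arms shifts the ratio, and the 90% interval moves with it.

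The ratio and its interval are the whole primary PK result, so a reader needs to know how far they depend on these judgements. The plan discloses which data were removed but never tabulates the ratio without the removals.

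**Working it through.** **Side by side.** The deviation-based exclusions have a list of candidate reasons (section 7.4) and a time limit (section 6.5.4). The blinded data review meeting in section 7.4 covers major deviations and per-protocol exclusions. The discretionary PK exclusions appear in neither place, so only the sentence in section 2 limits when they are made. Section 4.1 makes the Spiriva arm open label, and no section keeps the PK Scientist or the sponsor from the allocation. The sensitivity analyses in section 9.6.2 concern trough FEV1 only, and every PK table uses the PK analysis set. No all-data PK ratio is therefore planned.

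**The plan's own figure.** Section 4.3.1 gives 28 per arm for trough FEV1 (150 mL, SD 170 mL, two-sided 5%, 90% power). The normal formula gives 2 × (1.960 + 1.282)² × (170/150)² = 27.0, and the noncentral t distribution gives power 0.900 at n = 28, so the figure reproduces. No PK variability or precision target is stated. I take 28 per arm from this section and assume a between-subject CV of 30%, 50% or 70%.

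**Shift in the ratio.** For lognormal data the log-scale SD is s = √ln(1 + CV²), which is 0.294, 0.472 and 0.631. The expected values of the three largest of 28 standard normal observations are 2.014, 1.581 and 1.327. Dropping the k highest multiplies the expected ratio by exp(−s × sum of the k largest / (28 − k)). At CV 50%:

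- k = 1: 0.472 × 2.014 / 27 = 0.035, a fall of 3.5%.
- k = 2: 0.472 × 3.595 / 26 = 0.065, a fall of 6.3%.
- k = 3: 0.472 × 4.922 / 25 = 0.093, a fall of 8.9%.

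Simulation gives the same values, and for the other CVs:

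| Highest profiles dropped from one GSP304 arm | CV 30% | CV 50% | CV 70% |
|---|---|---|---|
| 1 | 2.2% | 3.5% | 4.6% |
| 2 | 4.0% | 6.3% | 8.4% |
| 3 | 5.6% | 8.9% | 11.7% |

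**Interval width.** Over four arms of 28 there are 4 × 28 − 4 = 108 residual degrees of freedom. The 90% limits lie a factor exp(t(0.95, 108) × s × √(2/28)) from the ratio. At CV 50% this is exp(1.659 × 0.472 × 0.267) = 1.233. After one to three removals the simulated factor is still about 1.23: the smaller residual variance is offset by the smaller arm.

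**Coverage.** With a true ratio of 100% and the four-arm ANOVA, the nominal 90% interval covers the truth in about 88%, 85% and 80% of trials after one, two and three removals, almost regardless of CV. Pooling variance over only the two arms compared gives about 88%, 84% and 79%. The loss comes from the shift, since the width hardly changes.

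**The case against.** A reader might infer that nothing stops these exclusions being made after unblinding. The document does not support that. Section 2 places all decisions on the final analysis before database lock, and a PKAS exclusion is such a decision. What stands is that this sentence is general. It does not say who is blinded, it protects less where the reference arm is open label, and the SAP departs from it for two exploratory analyses (PK/GFR in section 6.7.6.2, nebulization duration in section 8.5), which the sponsor may decide on after seeing end-of-study output.

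A second tempting reading is that exclusions would be hidden. They would not be: the study report must discuss them, and Listing 16.2.6.2.4 gives value and reason. Together with the by-subject Table 14.2.4.1, a reader could rebuild the all-data ratio wherever a parameter was derived. The plan does not do so itself.

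The scope also needs care. The sentence in section 6.5.4 does not say that exclusions follow inspection of the values; its defect is that it states no criterion. The section 6.7.6.1 rule removes single points between two unquantifiable values, not profiles, so the calculation above does not describe it. The plasma/urine rule requires investigation first and allows flagging instead of exclusion.

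Finally, nothing suggests that anyone would remove only the highest profiles from one arm. At CV 50% even that shift (3.5% to 8.9%) lies well inside the interval half-width of about 23%. With no PK test and no equivalence limits in section 8.4, no pass or fail result can be reversed. All of this limits the consequence to estimation.

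**Conclusion.** The point holds in a limited form. The SAP permits outcome-dependent removal of data from a primary analysis without an objective criterion, relies on one general sentence for timing, and plans nothing to show the effect on the CmaxSS and AUC0-tauSS ratios.

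Under lognormal data, 28 per arm and an assumed CV of 30% to 70%, a directed removal of one to three profiles from one GSP304 arm lowers the ratio by about 2% to 12% and reduces 90% coverage to about 88% to 80%. This is a bound on what such removals could do, not a forecast. It would be wrong to say that the interval becomes too narrow: its width is essentially unchanged, and the harm is a shifted estimate. Disclosure and the absence of a formal PK test keep the point moderate, but the remedy is cheap enough that it should be adopted.

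**What to change.** 1. Add to section 8.4 a sensitivity analysis that repeats the ANOVA and Table 14.2.5 on all treated non-placebo subjects with a derivable CmaxSS or AUC0-tauSS, and report both sets of ratios with their 90% intervals.
2. State in section 6.5.4 that any exclusion beyond the protocol-deviation exclusions already planned needs a documented dosing, sampling or assay reason. The deviation-based exclusions, for example for prohibited medication or eligibility, stay as they are.
3. State that these exclusions, and those under sections 6.7.6.1 and 6.7.6.2, are fixed and recorded before database lock by someone without the treatment allocation.

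While section 6.5.4 is open, correct its pointer to section 7.3, which is Screen Failures; deviations are in section 7.4. Section 7.4 itself says that major deviations both will and may lead to exclusion, and should say one.

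The cost is one extra table and a blinded PK review step. Because the Spiriva arm is open label, that step needs someone outside study conduct. CmaxSS and AUC0-tauSS can be derived without knowing the dose; only Fe% and the dose-normalized parameters need it. No sample size or data collection changes.
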